#### **9.8.4 Blood samples for serum bone turnover markers**

In Parts A, B, and C, whole blood samples of approximately 4mL per time point will be collected and processed to serum for analysis of circulating markers of bone turnover. Sampling time points throughout the study are outlined in the Schedules of Activities for Part A (Table 1-4), Part B (Table 1-7), and Part C (Table 1-8).

Sampling collection time points relative to dosing are detailed for Part A in Table 9-15 and for Parts B and C in Table 9-16.

Instructions pertaining to sample collection processing, storage, labeling, and shipping are provided in the laboratory manual for this study.

**Table 9-15: Blood samples for serum bone turnover markers in Part A**

Cycle	Day	Sampling time relative to dosing	Sampling time
Cycle 1	Day 1	Baseline	Predose
	Day 15	Within 0.5h prior to dosing	Predose
Subsequent cycles (up to and including Cycle 4)	Day 1	Within 0.5h prior to dosing	Predose
SFU Visit	On day of visit	On day of visit	NA

h=hour; NA=not applicable; SFU=Safety Follow-Up

**Table 9-16: Blood samples for serum bone turnover markers in Parts B and C**

Cycle	Day	Sampling time relative to dosing with UCB6114	Sampling time
Cycle 1	Day 1	Baseline	Predose
	Day 15	Within 0.5h prior to dosing	Predose
Cycle 2	Day 1	Within 0.5h prior to dosing	Predose
	Day 15	Within 0.5h prior to dosing	Predose
Subsequent cycles (from cycle 3 onwards)	Day 1	Within 0.5h prior to dosing	Predose
SFU Visit	On day of visit	On day of visit	NA

h=hour; NA=not applicable; SFU=Safety Follow-Up

### 9.8.5 Urine samples for urinary bone turnover markers

In Parts A, B, and C, urine samples of approximately 30mL per time point will be collected for analysis of urinary markers of bone turnover. Sampling time points throughout the study are outlined in the Schedules of Activities for Part A ([Table 1-4](#)), Part B ([Table 1-7](#)), and Part C ([Table 1-8](#)).

Sampling collection times relative to dosing are detailed for Part A in [Table 9-17](#) and for Parts B and C in [Table 9-18](#).

Instructions pertaining to sample collection processing, storage, labeling, and shipping are provided in the laboratory manual for this study.

**Table 9-17: Urine samples for urinary bone turnover markers in Part A**

Cycle	Day	Sampling time relative to dosing	Sampling time
Cycle 1	Day 1	Baseline	Predose
	Day 15	Within 0.5h prior to dosing	Predose
Subsequent cycles (up to and including Cycle 4)	Day 1	Within 0.5h prior to dosing	Predose
SFU Visit	On day of visit	On day of visit	NA

h=hour; NA=not applicable; SFU=Safety Follow-Up

**Table 9-18: Urine samples for urinary bone turnover markers in Parts B and C**

Cycle	Day	Sampling time relative to dosing with UCB6114	Sampling time
Cycle 1	Day 1	Baseline	Predose
	Day 15	Within 0.5h prior to dosing	Predose
Cycle 2	Day 1	Within 0.5h prior to dosing	Predose
	Day 15	Within 0.5h prior to dosing	Predose
Subsequent cycles (from cycle 3 onwards)	Day 1	Within 0.5h prior to dosing	Predose
SFU Visit	On day of visit	On day of visit	NA

h=hour; NA=not applicable; SFU=Safety Follow-Up

### 9.8.6 Blood samples for genetic analysis

An 8.5mL blood sample will be taken predose Cycle 1 Day 1 (Part A) or at Screening (Part A1, Part B and Part C) for genetic analysis as described in Section 9.7.

Instructions pertaining to sample collection, processing, storage, labeling, and shipping are provided in the laboratory manual for this study. A description of genetic analyses performed in this study is provided in Appendix 5 (Section 11.5).

### 9.8.7 Tumor biopsy for PD assessments and predictive biomarker assessments

In participants with a tumor that is accessible to biopsy and who have given informed consent, biopsies may be performed unless tissue collection carries a high risk of mortality or is otherwise contraindicated (to be determined at the discretion of the investigator).

- During Part A, these biopsies will be optional and collected at Screening and on Day 22.
- During Part A1, these biopsies will be mandatory and collected at the following time points:
  - After eligibility assessment and before study drug administration (Baseline) between Day-28 and Day -1.

- Within 2 weeks post Cycle 1 Day 15 for 2- or 4- weekly dosing schedule (ie, between Cycle 1 Day 15 and Cycle 2 Day 1 for Cohorts 1, 2 and 4) and within 2 weeks post Cycle 2 Day 1 for a 3-weekly dosing schedule (ie, between Cycle 2 Day 1 and Cycle 2 Day 15 for Cohort 3).

*Note: An additional blood sample each for PK and cGremlin-1 should be collected on the day of biopsy but only in cases where samples for these endpoints are not already scheduled to be taken on the Day.*

In addition, if a historical tumor biopsy specimen had been obtained prior to the study participant's entry into the study (eg, time of diagnosis), permission will be requested at the time of informed consent to use the biopsy for PD analysis.

- Tumor biopsies will not be obtained in Part B or Part C.

Biopsies will be performed according to standard clinical practice for the participant's indication and will be collected as outlined in the Schedules of Activities for Part A and Part A1 (Section 1.3).

Biopsy samples may be processed to RNA and/or formalin fixed and paraffin embedded. Ribonucleic acid samples may be used for transcriptomic analysis. Formalin-fixed and paraffin-embedded tissue may be used for transcriptomic analysis, immunohistochemistry, and/or protein expression analysis.

Excess tumor samples that remain after PD assessments have been performed may be retained while research on UCB6114 or study medications of this class continues, but no longer than 20 years (or other period according to local regulations). Tumor samples may be analyzed for additional biomarkers specifically related to the mechanism of action of UCB6114 or cancer biology as warranted by new preclinical discoveries and reports in the scientific literature.

### **Biopsy procedure in Part A1**

The most suitable lesion(s) to be biopsied should be discussed between the oncologist, radiologist, and/or colleague performing biopsy of cutaneous metastases or endoscopic biopsy, as appropriate.

Tumor biopsies are mandatory, however biopsies are to be performed, and the potentially required local anesthesia administered, only if considered to be of low risk to the participant, as determined by the Investigator and the health care professional performing the biopsy.

It is preferred that up to 5 cores per biopsy, 18-gauge in diameter and  $\geq 1$  cm in length will be obtained during each procedure, if considered safe and feasible. A single baseline biopsy core transferred to neutral buffered formalin (NBF) will constitute a successful biopsy. If an initial attempt at a biopsy is unsuccessful, the patient will be given an option to proceed with a repeated attempt. If the baseline biopsy remains unsuccessful no further biopsies will be performed but the patient may remain on the study and receive study medication.

If the study participant chooses not to undergo biopsies subsequent to the baseline biopsy, he/she will be withdrawn from the study. Feasibility for the subsequent biopsies will be assessed by the Investigator/the health care professional performing the biopsy and should include a consideration of patient safety. If the subsequent biopsy is deemed to be unsafe and/or not feasible, the study participant may remain on study and receive study medication.

The lesion from which each biopsy is taken will be documented in the Tissue Acquisition Form, and, if possible, an attempt will be made to collect the on-treatment biopsies from the same lesion as the Baseline biopsy.

The use of imaging to facilitate biopsies will be decided by members of the Interventional Radiology team and may include ultrasound, CT scan, or MRI. Should a CT scan be needed for biopsy, the number of scans for each procedure will be limited to the minimum number and duration required to safely obtain the biopsy.

Instructions pertaining to sample collection, processing, storage, labeling, and shipping are provided in the biopsy manual for this study.

#### **9.8.8        Historical tumor samples**

If available, samples from study participants' stored historical tumor biopsy specimen from the time of diagnosis or subsequent surgery may be sent to the analyzing laboratory. These samples will be analyzed for transcriptional and/or protein expression and the results may be compared with those obtained from the on-study biopsies where available.

#### **9.9        Biomarkers**

Collection of samples for other biomarker research is also part of this study and is described in Section 9.8.

Planned tertiary/exploratory biomarker assessments for Parts D, E, F, and G will be defined in a protocol amendment.

#### **9.10        Immunogenicity**

Antibodies to UCB6114 will be evaluated in serum samples collected from all participants according to the Schedules of Activities for Part A ([Table 1-4](#)), Part A1 ([Table 1-5 and Table 1-6](#)), Part B ([Table 1-7](#)), and Part C ([Table 1-8](#)). On dosing days, these samples will be collected predose. These samples will be tested by the Sponsor or Sponsor's designee. All tertiary/exploratory ADA assessments for Parts D, E, F, and G will be described in a protocol amendment.

Serum samples will be screened for antibodies binding to UCB6114 and the titer of confirmed positive samples will be reported.

The detection and characterization of antibodies to UCB6114 will be performed using validated assays by or under the supervision of the Sponsor.

In Part A, a total of 3 samples of 5mL of blood will be collected for ADA analysis during the first cycle of treatment, for a total of 15mL ([Table 9-19](#)). One sample of 5mL of blood will be collected for ADA analysis during Cycles 2, 3, and 4. If a participant continues on study beyond Cycle 4, an additional 5mL blood sample for ADA analysis (with concomitant sample for PK analysis) will be collected every 3 months (Cycle 7, Cycle 10, etc). An additional 5mL blood sample for ADA will be taken at the SFU Visit.

In Part A1, 1 sample of 5mL of blood will be collected for ADA analysis on Day 1 of the first 3 cycles (Cycles 1 to 3) and on Day 1 of every third cycles thereafter (ie, Cycle 6, Cycle 9; [Table 9-20](#)). An additional 5mL blood sample for ADA will also be taken at the SFU Visit.

In Part B and Part C, 1 sample of 5mL of blood will be collected for ADA analysis during Cycle 1 and Cycle 2 (Table 9-21). From Cycle 3 onwards, an additional 5mL sample for ADA analysis (concomitant to a sample for PK analysis) will be collected in even-numbered cycles only (Cycle 4, Cycle 6, etc). An additional 5mL blood sample for ADA will also be taken at the SFU Visit.

Instructions pertaining to sample collection, processing, storage, labeling, and shipping are provided in the laboratory manual for this study.

**Table 9-19: Blood sample time points for ADA analysis in Part A**

Cycle	Day	Sampling time relative to dosing	Sampling time
Cycle 1	Day 1	Baseline	Predose
	Day 15	Within 0.5h prior to dosing	Predose
	Day 22	On day of visit (taken at same time $\pm$ 5min as PK sample is collected)	On day of visit
Cycle 2	Day 1	Within 0.5h prior to dosing	Predose
Cycle 3	Day 1	Within 0.5h prior to dosing	Predose
Cycle 4	Day 1	Within 0.5h prior to dosing	Predose
Cycle 7 (onward)	Every 3 months	Within 0.5h prior to dosing	Predose
SFU Visit	On day of visit	On day of visit	NA

ADA=antidrug antibody; h=hour; NA=not applicable; SFU=Safety Follow-up

**Table 9-20: Blood sample time points for ADA analysis in Part A1**

Cycle	Day	Sampling time relative to dosing with UCB6114	Sampling time
Cycle 1	Day 1	Baseline	Predose
Cycle 2	Day 1	Within 0.5h prior to dosing	Predose
Cycle 3 a onwards	Day 1	Within 0.5h prior to dosing	Predose
SFU Visit	On day of visit	NA	On day of visit

ADA=antidrug antibody; h=hour; NA=not applicable; SFU=Safety Follow-Up

a Cycle 3 and every third cycle thereafter (ie, Cycle 6, Cycle 9 etc.)

**Table 9-21: Blood sample time points for ADA analysis in Part B and Part C**

Cycle	Day	Sampling time relative to dosing with UCB6114	Sampling time
Cycle 1	Day 1	Baseline	Predose
Cycle 2	Day 1	Within 0.5h prior to dosing	Predose
Cycle 3 (onward) a	Day 1	Within 0.5h prior to dosing	Predose
SFU Visit	On day of visit	NA	On day of visit

ADA=antidrug antibody; h=hour; NA=not applicable; SFU=Safety Follow-Up

a To be completed in cycle 3 and thereafter in even cycles only (i.e., Cycle 4, 6).

## **10 STATISTICAL CONSIDERATIONS**

A description of statistical methods follows and further details will be included in the Statistical Analysis Plan for each module.

### **10.1 Definition of analysis sets**

#### **Enrolled Set**

The Enrolled Set (ES) consists of all study participants who sign the Informed Consent Form.

#### **Safety Set**

The Safety Set (SS) will be used primarily for the analysis of safety data and will consist of all study participants who receive 1 or more full or partial doses of any study treatment.

#### **Per-protocol Set**

The Per-protocol Set (PPS) will include all study participants in the SS who do not have important protocol deviations that may substantially affect antitumor activity. The PPS will be the primary analysis set for the analysis of the exploratory antitumor activity endpoints.

#### **Pharmacokinetic Set**

The Pharmacokinetic Set (PKS) will include all study participants in the SS who have at least 1 evaluable PK concentration (ie, a sample which is above the lower limit of quantitation and for which the date and time of the sample and prior date and time of dosing are known). Additional participants or specific samples may be excluded from the PKS at the discretion of the Advanced Modeling and Simulation Scientist/Quantitative Clinical Pharmacology scientist.

Pharmacokinetic analysis will be performed on the PKS.

#### **ADA Set**

The ADA Set (ADAS) will include all study participants in the SS who have at least 1 evaluable ADA assessment.

Immunogenicity analyses will be performed on the ADAS.

## Pharmacodynamic Set

The Pharmacodynamic Set (PDS) will include all study participants in the SS who have at least 1 evaluable PD assessment (where appropriate, the sample should be above the lower limit of quantitation and the date and time of the sample should be known).

Pharmacodynamic analysis will be performed on the PDS.

## DLT Evaluatable Set

The DLT Evaluatable Set (DES) will include all study participants who, during the DLT assessment period:

- Receive the planned dose of UCB6114 (Part A and Part A1)
- Receive the planned dose of UCB6114 and at least 80% of the planned dose of TFD/TPI (Part B)
- Receive the planned dose of UCB6114 and at least 80% of the planned dose of mFOLFOX6 (Part C)
- Stopped treatment because of a DLT (any part of the study)

The DES will be used by the SMC for all dose escalation/de-escalation decision making.

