#### **4.1.2 Part A – Monotherapy dose escalation**

In Part A of the study, 3 to 6 participants will be enrolled per dose level using a modified rolling-6 design. The rolling-6 design is an algorithm-based design in which a total of 6 participants can be enrolled at the same dose level. The modification requires that each dose level incorporates a sentinel participant. The enrollment of a sentinel participant in each cohort has been included as an additional risk mitigation measure to monitor infusion related reactions and other early onset treatment related AEs. Each sentinel participant will be assessed for at least 24 hours following second treatment administration before further participants within the dose

cohort can be enrolled. In the absence of a DLT observation in the sentinel participant after 16 days, the remaining 5 participants may be enrolled concurrently ([Figure 4-1](#)). Should the sentinel participant experience a DLT, then participants 2 and 3 will be enrolled and observed for 16 days ([Figure 4-2](#)). Escalation can be performed when 3/3, 4/4, 5/5, 5/6, or 6/6 participants are evaluated without a DLT. When a single DLT has been observed in a given dose level, participants will be included at the same dose level, up to a total of 6 participants. De-escalation occurs when 2 or more participants experience a DLT at the first dose level.

Dose escalation requires at least 3 participants to be treated and observed for at least 28 days after the first dose (assuming UCB6114 is dosed Q2W). If dosing is less frequent (due to missed or delayed doses or due to a planned change in schedule), at least 3 participants should be treated and observed for a minimum of 28 days (ie, 1 cycle), before dose escalation is considered. The second participant in any new cohort should also not be dosed until the first participant has received at least 2 doses and been observed for a minimum of 16 days (ie, 24 hours following the second treatment administration). All participants will remain in the hospital or study site's standard monitoring facility for continuous monitoring for the first 24 hours following the first dose; at subsequent doses, the participant may remain at the hospital or study site's standard monitoring facility at the investigator's discretion.

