#### **4.1.2.2 Dose escalation criteria**

Dose-limiting toxicities observed in the full 28 days of Cycle 1 will be used to decide whether escalation to the next dose level may take place or whether cohort expansion or dose de-escalation should occur. However, all available safety data (both within the cohort and from preceding cohorts) will be taken into consideration when making such decisions.

Dose-limiting toxicities may not be encountered in this study. There is no intention to continue dose escalation until an MTD can be established. The decision-making guidelines for dose escalation are shown in [Figure 4-1](#) (no DLT was observed in the sentinel participant) and [Figure 4-2](#) (a DLT was observed in the sentinel participant). The SMC will make dose escalation decisions based upon review of safety data and available PK data after all participants in a cohort complete at least the first treatment cycle (28 days) or have discontinued.

[figure not shown]

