## **10.6 Handling of dropouts or missing data**

Participants who withdraw from the study before receiving study medication will be replaced and will not be included in the safety or antitumor activity assessments. Safety analyses will be conducted on all participants who have received at least 1 dose of the study medication, regardless of whether they are deemed evaluable for the assessment of a dose level (ie, they receive the planned dose during Cycle 1 [2 treatment administrations]).

Any participant who is discontinued from the study before receiving all doses of UCB6114 in Cycle 1 will be deemed nonevaluable for assessment of a dose level and will be replaced unless they experience a DLT before withdrawal.

In the context of the COVID-19 pandemic, participants who miss doses due to a positive COVID-19 diagnosis or known or expected exposure may continue in the study if, in the opinion of the investigator, they are experiencing clinical benefit and it is in their best interest to continue treatment (see Section 7.1.4).

Nonevaluable participants may be replaced to ensure that at least 3 participants receive all assigned doses of therapy at each dose level/cohort, unless accrual to that cohort has stopped due to DLTs.

Further details on any imputation of missing data will be included in the SAPs for each module.

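### DLT evaluability depends on doses received, not on observation to the end of the DLT window, so a fully dosed participant lost early counts as DLT-free and is not replaced

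*Protocol*

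**What the plan says.** Section 10.1 gives three routes into the DES:

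- Parts A and A1: "Receive the planned dose of UCB6114 (Part A and Part A1".
- Part B: "Receive the planned dose of UCB6114 and at least 80% of the planned dose of TFD/TPI (Part B". Part C has the same form with mFOLFOX6.
- Any part: "Stopped treatment because of a DLT (any part of the study".

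None sets a minimum observation time. The set is operative during the trial: "The DES will be used by the SMC for all dose escalation/de-escalation decision making".

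Section 10.6 follows the same logic. "Any participant who is discontinued from the study before receiving all doses of UCB6114 in Cycle 1 will be deemed nonevaluable", and is replaced unless a DLT came first. Its gloss on evaluability is also about doses: "they receive the planned dose during Cycle 1 [2 treatment administrations".

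Elsewhere the protocol works with 28 days:

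- The DLT window is the whole of Cycle 1, 28 days, in Part A (4.1.2.2) and Days 1 to 28 in Parts B and C (4.1.4.2.1, 4.1.5.2.1).
- In Part A, "Dose escalation requires at least 3 participants to be treated and observed for at least 28 days after the first dose" (4.1.2). The SMC may nevertheless decide once all participants "complete at least the first treatment cycle (28 days) or have discontinued" (4.1.2.2).
- Sections 4.1, 4.1.4 and 4.1.5 time the decision on the next cohort to when everyone in the preceding cohort has been monitored for 28 days. Sections 4.1.4.3 and 4.1.5.3 expect DLT-evaluable participants to have completed 28 days of treatment.
- Section 4.1.3 times the Part A1 SMC reviews by a 28-day observation period.

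**The concern.** DLT incidence is a primary endpoint in Parts A, A1, B and C, and 10.3.1 estimates it as a crude proportion. In such a proportion, a participant who was not watched to the end of the window contributes a full unit to the denominator and can contribute nothing further to the numerator. Time not observed is scored as time without a DLT.

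The rules in 10.1 and 10.6 allow exactly this for a participant who has had all Cycle 1 doses and then leaves observation. No section removes or replaces that person; the other replacement rule (6.6.1.2 and 7.1.4) is also triggered by a missed dose. The error has one direction: it makes a dose or schedule look safer than it is. With 3 to 9 participants per dose level in Parts B and C, one person can decide the outcome.

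**Working it through.** **1. How much of the window can be lost.** On Q2W dosing the last Cycle 1 infusion is on Day 15 (1.1, 4.3.3.1), so 28 − 15 = 13 of 28 days can go unobserved. In Part A1 Cohort 4 the only Cycle 1 infusion is on Day 1 (Figure 1-3), so 28 − 1 = 27 of 28 days can. Cohort 3 also has a single Cycle 1 infusion, on Day 1 of a 21-day cycle. The two-administration gloss in 10.6 fits neither cohort.

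**2. Reproducing the plan's decision table.** Inputs from 4.1.4: target 0.25, equivalence interval 0.20 to 0.30. Assumed, because the protocol does not state them: a Beta(1,1) prior, and DR when P(p > 0.25 | data) > 0.95. With x DLTs in n, the posterior is Beta(1+x, 1+n−x). The decision is the interval with the largest posterior probability per unit length. Every filled cell of Table 4-2 (identical to Table 4-3) is reproduced.

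**3. Removing one unobserved, DLT-free participant.** Compare the cell x/n with x/(n−1):

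| Counted under 10.1 | Leaver excluded |
|---|---|
| 1/7: E | 1/6: S |
| 2/5: S | 2/4: D |
| 3/7: S | 3/6: D |
| 3/6: D | 3/5: DR |
| 4/9: D | 4/8: DR |

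For the first row, at 1/7 the posterior is Beta(2,7), with P(p<0.20) = 0.4967 and P(p<0.30) = 0.7447. The unit masses are 0.4967/0.20 = 2.483 (escalate), (0.7447 − 0.4967)/0.10 = 2.480 (stay) and 0.2553/0.70 = 0.365 (de-escalate). At 1/6 they are 2.116, 2.473 and 0.471, so the decision is to stay. Every change is in the cautious direction. In addition, 0/3 (escalate) becomes 0/2, below the minimum of 3 evaluable participants per dose level in 4.1.4 and 4.1.5. These shifts come from the printed tables and need no assumption about dropout or DLT timing.

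**4. Part A.** The requirement in 4.1.2 protects three participants. It does not cover participants 4 to 6. If one of the five DLT-free participants in a 5/6 result left early, the observed result is 4/5, which is not among the escalation conditions in 4.1.2.

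**5. Part A1.** Section 4.1.3 stops a cohort on a count of 3 or more participants with DLTs, with 8 per cohort. Take a true rate of 40%, DLT onset uniform over 28 days, and k participants gone on Day 2, each with an observable rate of 0.40 × 2/28 = 0.029. P(≥3 DLTs) is then 68.5% (k = 0), 58.8% (k = 1) and 47.3% (k = 2). With seven fully observed participants and no leaver it is 58.0%. Excluding the leaver without replacement therefore recovers nothing; only replacement restores 68.5%.

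**6. Illustration of size in a three-participant mTPI cohort.** Assume uniform onset and k participants gone on Day 16. P(0 of 3) = (1−p)^(3−k) × (1 − p × 16/28)^k.

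| True rate p | k = 0 | k = 1 | k = 2 |
|---|---|---|---|
| 0.40 | 21.6% | 27.8% | 35.7% |
| 0.50 | 12.5% | 17.9% | 25.5% |

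**7. Illustration averaged over participants.** Let a share f leave and lose a share q of their DLT risk, so the observed rate is p × (1 − f × q). At p = 0.33:

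| f, q | Observed rate | P(≤1 DLT in 6) | P(≥3 DLTs in 8) |
|---|---|---|---|
| none | 33.0% | 35.8% | 52.4% |
| 10%, 0.5 | 31.4% | 39.1% | 48.2% |
| 20%, 0.5 | 29.7% | 42.7% | 44.1% |
| 20%, 1 | 26.4% | 50.1% | 35.7% |

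The values of f, q, k and the onset pattern in steps 5 to 7 are assumptions, not protocol figures.

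**The case against.** The best reply is that the protocol plainly intends 28 days of monitoring. Sections 4.1, 4.1.4 and 4.1.5 say that the decision on the next cohort waits until everyone has been monitored that long, and 4.1.4.1 and 4.1.5.1 convene the SMC after the last participant completes the DLT observation period. Read strictly, a cohort with a Day-16 leaver could not produce a decision in Part B or C. This stands as evidence of intent. But those passages say when a decision is taken. They do not say who is in the denominator, or what happens when a participant cannot be monitored, and 10.1 and 10.6 answer both questions on doses alone. The result is a contradiction to reconcile.

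A reader might infer that anyone who progresses or stops treatment after the last Cycle 1 dose becomes an unobserved non-event. The documents do not support that. AEs are recorded to 30 days after the last dose (Schedules of Activities, 1.3), which reaches about Day 45 after a Day 15 dose and about Day 31 after a Day 1 dose. Only consent withdrawal, loss to follow-up, or a death not counted as a DLT cuts the window short. Section 7.2 also has sites pursue participants who withdraw, unless they refuse follow-up.

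Decisions are also not mechanical. Table 4-2 informs the SMC, which adjudicates DLTs, weighs all available safety data and may notice a short follow-up. In Part A1 a single DLT already triggers an ad hoc meeting. These points reduce how often the gap would matter; they do not repair the definition.

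**Conclusion.** The point holds in a limited form. Sections 10.1 and 10.6 define evaluability and replacement by doses received, while the endpoint is defined over 28 days and the decision-timing sections presume 28 days of monitoring. A fully dosed, DLT-free participant lost to observation before the window closes is counted as a non-event and not replaced, and the bias runs only toward escalation or acceptance of a schedule.

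The firm part of the size is structural: five cells of Tables 4-2 and 4-3 change with one such participant, 0/3 falls below the evaluable minimum, and up to 13 of 28 days (Q2W) or 27 of 28 (Part A1 Cohort 4) can be missed. In Part A1 the harm is lost information because the leaver is not replaced, not a distorted denominator.

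It would be tempting to conclude that early departure is frequent in this population and that the percentages above are expected effects. The protocol gives no departure rate and no DLT onset distribution, so they are illustrations only.

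**What to change.** - **10.1:** define the DES as participants who either (a) received the required Cycle 1 treatment and were followed for safety through the full DLT assessment period, or (b) had a DLT.
- **10.6:** make a fully dosed participant whose observation ends before the window closes, without a DLT, nonevaluable and replaceable.
- **4.1.2.2:** keep the allowance for participants who have discontinued, but state that those who discontinued without a DLT and without complete DLT-window follow-up are not counted as evaluable. Deleting the allowance outright would block a decision when someone stops because of a DLT, since that person cannot complete the cycle and is not replaced.
- Reconcile 10.1 and 10.6 with 4.1, 4.1.2, 4.1.4, 4.1.4.3, 4.1.5 and 4.1.5.3, and carry the same definition into the SMC charter.

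The cost is wording, an occasional replacement participant and a slightly longer cohort. Section 10.6 already provides for replacement, and 10.8.1 allows for it in the Part A sample size.
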